# 9.4.4 SAFETY ANALYSES

We will monitor the toxicity events for the expansion cohort for every 2 patients after the first 3 patients. We will apply a Bayesian toxicity monitoring rule: if the posterior probability of experiencing DLT exceeding 0.25 is greater than 65%, we will hold the enrollment for reviewing the MTD. The prior distribution for this monitoring rule is a beta,(1,5) which translates to a 90% probability of DLT being between 1% and 45.1%. The stopping rules for toxicity monitoring and operating characteristics for expansion cohort are listed in the following:

Table 1: Early stopping rule for monitoring toxicity

Number of Patients	3	4-6	7-10
Number of Patients with DLT resulting in escalation suspension	2	3	4

Table 2: Operating Characteristics of stopping rule for toxicity, based on 50,000 simulations:

True Toxicity Rate	Probability of declaring treatment too toxic	Average sample size
15%	7.1%	9.8
20%	15.3%	9.5
25%	26.5%	9.2
30%	39.6%	8.7
35%	52.9%	8.2
40%	65.4%	7.7
45%	76%	7.2

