### 6.1.4 DEFINITION OF DOSE-LIMITING TOXICITY

Number of Patients with DLT at a Given Dose Level	Escalation Decision Rule	
0 out of 3	Enter 3 patients at the next dose level.	
≥ 2	Dose escalation will be stopped. This dose level will be declared the maximally administered dose <highest administered="" dose="">. Three (3 additional patients will be entered at the next lowest dose level if or 3 patients were treated previously at that dose.</highest>	
1 out of 3	
 
Enter at least 3 more patients at this dose level.
 
If 0 of these 3 patients experience DLT, proceed to the next dose level.
 
If 1 or more of this group experience DLT, then dose escalation is stopped, and this dose is declared the maximally administered dose. Three (3) additional patients will be entered at the next lowest dose level if only 3 patients were treated previously at that dose.
 
	
≤ 1 out of 6 at highest dose level below the maximally administered dose	This is generally the recommended phase II dose. At least 6 patients must be entered at the recommended phase II dose.	

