### **Dose-Expansion Cohorts**

Once the RP2D is reached, a total of10 patients will be treated at this dose. For the expansion cohort, patients will continue to be monitored for occurrence of DLT. If 2 of the first 5 patients or if  $\geq$  2 of 6 patients experience DLT, the PI will discuss with all study investigators and with CTEP whether further addition of patients is needed to reassess the RP2D.

Monitoring of safety and toxicity data will be captured in OnCore, Moffitt's clinical trials database.

Dose-limiting toxicities are defined as any of the following that is at least possibly attributable to the investigational treatment:

- 1. Grade 2-4 infusion toxicity
- 2. Grade 4 organ toxicity (as defined by NCI CTCAE v 5.0), not preexisting, not due to the primary malignancy, and not due to chemotherapy or infection
- 3. Grade 3 organ toxicity that does not resolve within 14 days and that is not preexisting, not due to the primary malignancy, and not due to chemotherapy or infection
- 4. Grade 2-4 acute GvHD
- Delayed neutrophil recovery: ANC >500/μl does not occur within 56 days AND measurable donor chimerism is >5%
- 6. Grade 3-4 cytokine release syndrome (CRS) (see Appendix C) (75)
  Any grade 5 reaction other than progressive disease

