# 9.4.3 ANALYSIS OF THE SECONDARY ENDPOINT(S)

The RP2D is defined as the dose level selected to be evaluated in the expansion cohort or future phase II studies and will be equivalent to the MTD determined in the Phase 1b portion of the study. Once we determine the RP2D level, we will enroll 10 additional eligible patients and treat with the RP2D level. The goal for this expansion cohort is to evaluate the safety and tolerability for patients who will be treated with NE-DLI in the RP2D dose level, and to evaluate the preliminary efficacy estimate for the ORR. Including the dose escalation portion in which 3 or 6 enrolled patients will have been treated at the RP2D level, a total of at least 13 patients will be treated at the RP2D level. Based on previous data, (99) the complete response rate using microtransplantation was in the range of 36%-52% for MDS or AML from antecedent MDS patients. Hence, for the phase 2 portion, an ORR of 45% is considered clinically meaningful. With a sample size of 13 patients, if our ORR is 45%, the 95% CI (exact binomial) will be (18-74%); if the ORR is 50%, the 95% CI will be (22-78%). The response rates, including ORR and hematologic response by IWG 2006 criteria will be estimated via an exact binomial test with 95% confidence interval in combining patients treated at the RP2D dose level and the expansion cohort patients.

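### Section 9.4.4 does not list its looks, and Table 2 cannot be the operating characteristics of a rule that includes Table 1's hold at 2 DLTs in 3 patients

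*Combined protocol and SAP*

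**What the plan says.** Section 9.4.4 describes monitoring only by frequency: "We will monitor the toxicity events for the expansion cohort for every 2 patients after the first 3 patients". The criterion is a posterior probability above 65% that the DLT rate exceeds 0.25, under a Beta(1,5) prior. When it is met, "we will hold the enrollment for reviewing the MTD".

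Table 1 gives the counts, under the row label "Number of Patients with DLT resulting in escalation suspension": 2 DLTs at 3 patients, 3 at 4–6 patients and 4 at 7–10 patients. The next table is headed "Table 2: Operating Characteristics of stopping rule for toxicity, based on 50,000 simulations" and gives the chance of declaring the treatment too toxic and the average sample size at true DLT rates of 15% to 45%.

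Section 9.4.3 sets the cohort size: "we will enroll 10 additional eligible patients and treat with the RP2D level".

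Two other passages may also act on DLTs in the expansion. The dose-expansion text in section 6.1.4 calls for a discussion among the investigators and with CTEP, with a trigger that begins "If 2 of the first 5 patients" and continues to 2 or more of 6. Appendix F suspends accrual when at least 2 of the first 6 patients on any dose level have a DLT.

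**The concern.** The monitoring sentence can mean looks at 3, 5, 7 and 9, a first look at 5, or looks at 4, 6, 8 and 10. The odd-numbered readings also leave open whether 10 is a look. Table 1 points to a look at 3, because its first column is a boundary there. Table 2 is presented as the performance of the same rule, yet its average sample sizes look too large for a rule that can hold after 3 patients.

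Two things are at stake. First, if 2 of the first 3 expansion patients have a DLT, staff cannot tell whether the Bayesian rule holds enrollment. It does if 3 is a look. Under 4, 6, 8, 10 it does not act at 3, and 2 of 4 is below the boundary. Second, anyone judging the rule from Table 2 sees the performance of one possible schedule, and not one that uses all of Table 1.

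A related gap is that the documents do not say how the section 9.4.4 hold, the section 6.1.4 discussion and the Appendix F suspension relate in the expansion cohort.

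**Working it through.** **Inputs.** From section 9.4.4: Beta(1,5) prior, DLT-rate limit 0.25, posterior threshold 0.65, and Tables 1 and 2. From section 9.4.3: 10 expansion patients. The calculations assume independent DLTs with a common probability, do not count escalation patients, and treat a hold as the end of enrollment when averaging sample size.

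**Step 1: Table 1 reproduces.** With x DLTs in n patients, the posterior is Beta(1 + x, 5 + n − x). P(rate > 0.25) is:
- 2 of 3: 0.679, hold
- 2 of 4: 0.601, no hold
- 3 of 6: 0.713, hold
- 3 of 7: 0.649, no hold
- 4 of 10: 0.687, hold

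The boundaries are correct.

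**Step 2: a cap that does not depend on the other looks.** If 2 or more DLTs in the first 3 patients stops enrollment, those cohorts have size 3 and all others at most 10. Hence average N ≤ 10 − 7 × P(2 or more of 3), where P = 3p²(1 − p) + p³. At p = 0.45, P = 0.425 and the cap is 10 − 7 × 0.425 = 7.02.

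| True rate | P(≥2 of 3) | Cap | Table 2 average N | Excess |
|---|---|---|---|---|
| 15% | 0.061 | 9.57 | 9.8 | 0.23 |
| 20% | 0.104 | 9.27 | 9.5 | 0.23 |
| 25% | 0.156 | 8.91 | 9.2 | 0.29 |
| 30% | 0.216 | 8.49 | 8.7 | 0.21 |
| 35% | 0.282 | 8.03 | 8.2 | 0.17 |
| 40% | 0.352 | 7.54 | 7.7 | 0.16 |
| 45% | 0.425 | 7.02 | 7.2 | 0.18 |

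Rounding accounts for at most 0.05, and simulation error for about 0.01.

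**Step 3: exact enumeration of schedules.** With Table 1's boundaries, all 255 non-empty sets of looks from 3 to 10 were evaluated. Chance of a hold (%):

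| True rate | Table 2 | 4,6,8,10 | 3,5,7,9,10 | 3,5,7,9 | 5,7,9,10 |
|---|---|---|---|---|---|
| 15% | 7.1 | 7.2 | 9.5 | 8.4 | 6.1 |
| 20% | 15.3 | 15.4 | 18.3 | 15.7 | 13.8 |
| 25% | 26.5 | 26.6 | 29.5 | 25.2 | 24.5 |
| 30% | 39.6 | 39.5 | 42.2 | 36.2 | 37.3 |
| 35% | 52.9 | 52.8 | 55.0 | 48.0 | 50.7 |
| 40% | 65.4 | 65.4 | 67.1 | 59.7 | 63.6 |
| 45% | 76 | 76.2 | 77.4 | 70.3 | 74.8 |

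Average N, in the same row order:
- 4,6,8,10: 9.78/9.53/9.18/8.75/8.26/7.72/7.17
- 3,5,7,9, with or without 10: 9.52/9.15/8.68/8.14/7.55/6.94/6.32
- 5,7,9,10: 9.84/9.65/9.36/8.99/8.55/8.07/7.57

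The simulation standard error at 50,000 runs is 0.1 to 0.2 points. Looks at 4, 6, 8, 10 therefore match Table 2 (largest misses 0.17 points and 0.06 patients). Among the 128 sets that include 3 with the 2-of-3 hold, the best still misses at least one printed probability by 2.49 points and, taken separately, at least one average N by 0.29. The probability check does not depend on treating a hold as the end of enrollment.

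Twelve sets fit within 0.2 points and 0.1 patients, and none contains 3. Besides 4,6,8,10 they include 4,6,9,10, 5,6,9,10 and a look after every patient from 5 to 10. A look at 3 can fit only if its boundary is changed to 3 of 3 (for example looks at 3,5,6,10), which contradicts Table 1. The schedule actually simulated is therefore an inference.

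**Step 4: size of the difference in conduct.** At a 25% rate, the chance of exactly 2 DLTs in the first 3 patients and none in the fourth is 3 × 0.25² × 0.75 × 0.75 = 10.5%. Under 4,6,8,10 such a cohort is never held if patients 5–6 have no DLT and patients 7–10 have at most one: 0.75² × (0.75⁴ + 4 × 0.25 × 0.75³) = 0.415. So 10.55% × 0.415 = 4.4% of cohorts are held at 3 on one reading and never held by the Bayesian rule on the other. Across true rates of 15% to 45% this figure runs 3.1/4.0/4.4/4.2/3.7/3.0/2.2%.

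**The case against.** The best defense is that 3 is not a look. On that view the sentence means looks in pairs once more than 3 patients are in, at 4, 6, 8 and 10. Table 2 is then right, and Table 1 is only a lookup of the boundary at each size; it also covers sizes that no two-patient schedule visits. This is tenable and cannot be excluded. It does not remove the problem: Table 1 is titled as an early stopping rule and starts with a stop at 3, and the sentence reads more naturally as 3, 5, 7, 9 or 5, 7, 9, none of which, with or without 10, reproduces Table 2.

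It is also fair that the differences are small for a 10-patient cohort, that Table 2 sets no sample size, and that the criterion itself is clear once a look is taken.

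Other safeguards exist. Every cohort with 2 DLTs in the first 3 meets the section 6.1.4 trigger, and sections 6.4 and 10.1.5 provide monthly meetings and continuous monitoring with bi-weekly group review. The 4.4% is therefore not the chance that nothing happens. But section 6.1.4 requires a discussion, not a hold.

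Whether Appendix F helps is uncertain, because it is headed as escalation criteria. Section 9.4.3 allows for "Including the dose escalation portion in which 3 or 6 enrolled patients will have been treated at the RP2D level". If Appendix F reaches the expansion and 3 were treated there, expansion patients 1–3 are patients 4–6 on that dose level, and 2 DLTs among them meet its suspension count. Section 6.1.4, however, says "At least 6 patients must be entered at the recommended phase II dose"; with 6 already treated, expansion patients fall outside the first 6.

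**Conclusion.** The concern holds. Tables 1 and 2 cannot both describe one operating rule, and the sentence that should settle the schedule does not. The average-N cap shows this whatever other looks are taken, under the assumptions listed with the inputs.

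The size is moderate. If 3, 5, 7, 9, 10 is meant, Table 2 understates the chance of a hold by 1.4 to 3.0 points and overstates average N by 0.3 to 0.9. If 5, 7, 9, 10 is meant, it overstates the chance of a hold by 1.0 to 2.3 points. If 4, 6, 8, 10 is meant, Table 2 is correct and the fault is an unlisted schedule with one unused boundary. The prior, threshold and Table 1 counts stand, and the MTD and ORR analyses are not affected.

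**What to change.** List the looks by patient number in section 9.4.4 and make both tables follow from that list. The choice is the sponsor's.

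- If 3 is a look, for example *after 3, 5, 7, 9 and 10 patients*: keep Table 1 and replace Table 2 with exact values for the chosen schedule. Those for this example are given above; the chance of a hold at a 15% rate would then print as 9.5% instead of 7.1%.
- If the looks are *after 4, 6, 8 and 10 patients*: keep Table 2, and delete Table 1's 3-patient column or mark it as not used.

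Also reconcile section 9.4.4, the dose-expansion text in section 6.1.4, and Appendix F. State how the three triggers relate in the expansion cohort, whether the Appendix F suspension applies there, and whether escalation patients treated at the RP2D count toward its first 6.

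The cost is one rewritten sentence, then seven table rows reprinted or one column annotated, plus one or two linking sentences.

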# 9.4.2 ANALYSIS OF THE PRIMARY ENDPOINT(S)

For the dose escalation portion, a minimum of two subjects and a maximum of 18 subjects will be enrolled. There will be three dose levels in the dose escalation portion. MTD is defined as the highest dose level with the probability of DLT less than 33% (DLT events are defined in Section 6). The DLT observation window will be until confirmation that the donor cells have been rejected (ANC ≥ 500/microL AND confirmation of either bone marrow donor chimerism <5% or donor blood CD3+ chimerism <5%) OR within 56 days following NE-DLI, whichever occurs first. Per the traditional 3+3 schema, up to three patients may be enrolled concurrently and treated at the same dose level. The first three patients will be treated at dose level 1. For each dose level, if none of three patients experiences a DLT, we will escalate to the next dose level until reaching dose level 3. For each dose level, if one of the three patients experiences a DLT, we will enroll three additional patients and treat at the same dose level. In this case, if none of these additional three patients experiences a DLT, we will escalate the dosage to next level until reaching dose level 3. For each dose level, if two or more patients among six enrolled patients experience a DLT, or two or more patients in the three patient cohort experience DLT, the dosage level exceeds the MTD and the previous dose level will be declared as the MTD. If the first dose level exceeds the MTD, the study will be suspended. If no subjects experience a DLT at any dose level, the MTD will be level 3 (5 x 10^7 CD4+ T cells/kg). Similarly, if exactly one of six patients enrolled at dose level 3 experiences a DLT, then the MTD will be dose level 3. All patients in a dose level must be observed through the DLT window prior to enrolling patients at a higher dose level.

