- 3. Grade 3 organ toxicity that does not resolve within 14 days and which is not preexisting, not due to the primary malignancy, and not due to chemotherapy or infection
- 4. Grade 2-4 acute GvHD
- Delayed neutrophil recovery: ANC>500/μl does not occur within 56 days AND measurable donor chimerism is >5%
- 6. Grade 3-4 CRS; see Appendix for grading scheme)
- 7. Any Grade 5 reaction other than progressive disease.

If 2 or more of the first 6 patients on any dose level experience DLTs, accrual to the trial will be suspended and the sponsor of the IDE (the PI) will initiate a formal consultation with the FDA in order to determine whether the

CD8-depleted non-engrafting HLA antigen-mismatched unrelated donor lymphocyte infusion... Protocol <20042> Version 10 29 March 2023

observed toxicities are or are not attributable to the device. Subsequent accrual to the trial may resume only with permission from the FDA. Any questions or concerns as to the relationship of grade > 3 toxicities to use of the investigational device will be discussed with the appropriate FDA Clinical Review Staff.

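### Section 9.4.4 has no expansion boundary before 3 patients, although 2 DLTs in the first 2 already exceed its own 65% criterion; the gap is open when 6 patients were already treated at the RP2D

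*Combined protocol and SAP*

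**What the plan says.** Section 9.4.3 plans an expansion in which "we will enroll 10 additional eligible patients and treat with the RP2D level". Section 9.4.4 sets the schedule, "We will monitor the toxicity events for the expansion cohort for every 2 patients after the first 3 patients", and the criterion, "if the posterior probability of experiencing DLT exceeding 0.25 is greater than 65%, we will hold the enrollment for reviewing the MTD". The prior is given as "The prior distribution for this monitoring rule is a beta,(1,5) which translates to a 90% probability of DLT being between 1% and 45.1"%. The Table 1 row "Number of Patients with DLT resulting in escalation suspension" lists 2 at 3 patients, 3 at 4-6 patients and 4 at 7-10 patients. It has no column for 1 or 2 patients.

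Two other rules can apply to the same patients:

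- Section 6.1.4, under Dose-Expansion Cohorts, starts from the condition "If 2 of the first 5 patients" (or at least 2 of 6) have a DLT. It then asks for a discussion among the investigators and CTEP on reassessing the RP2D. It states no hold.
- Appendix F says: "If 2 or more of the first 6 patients on any dose level experience DLTs, accrual to the trial will be suspended".

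Section 9.4.3 expects that 3 or 6 patients will have been treated at the RP2D before the expansion starts. The Section 6.1.4 table asks for at least 6 at that dose.

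**The concern.** The hold criterion is a statement about the posterior, so it can be evaluated after any number of patients. Table 1 leaves out the one earlier point at which it can be met: 2 DLTs in the first 2 expansion patients. Read alone, Section 9.4.4 then lets a third patient be infused at a dose for which the plan's own threshold has been crossed, and that patient's outcome cannot alter the hold at 3. At stake is one patient's exposure that contributes nothing to the monitoring decision.

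**Working it through.** **Inputs.** Section 9.4.4: prior Beta(1,5), DLT-rate threshold 0.25, cut-off 0.65, Tables 1 and 2. Section 9.4.3: 10 expansion patients, with 3 or 6 treated earlier at the RP2D. Section 4.4: one patient per 5-6 weeks. Section 9.4.2: DLT window of up to 56 days.

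**Formula.** After x DLTs in n patients the posterior is Beta(1+x, 5+n-x), and P(rate > 0.25) = P(Bin(5+n, 0.25) ≤ x).

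**The plan's own figures first.** The prior's 5th and 95th percentiles are 1 - 0.95^(1/5) = 1.02% and 1 - 0.05^(1/5) = 45.07%, as stated. Every Table 1 boundary is reproduced:

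- 2/3 gives 0.679 (hold).
- 2/4 gives 0.601 (no hold) and 3/4 gives 0.834.
- 3/6 gives 0.713 (hold).
- 3/7 gives 0.649 (no hold) and 4/7 gives 0.842.
- 4/10 gives 0.687 (hold).

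**Before 3 patients.** 1/1 gives 0.534, so there is no boundary at n=1. For 2/2, P(Bin(7, 0.25) ≤ 2) = 0.1335 + 0.3115 + 0.3115 = 0.756, above 0.65. The criterion therefore implies a bound of 2 at n=2.

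**After 2/2.** Patient 3 leads to 2/3 (0.679) or 3/3 (0.886). Both are holds, so with a look at 3 the hold is certain.

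**Size under the stated schedule.** The path 2/2 has probability p² at true DLT rate p. A bound at n=2 stops that path one patient sooner and changes no decision. The saving is therefore p² patients: 0.15² = 0.02, 0.25² = 0.06, 0.30² = 0.09, 0.45² = 0.20.

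**Operating characteristics.** Exact recursion over binomial paths to n=10, with Table 1 bounds and bound 2 at n=2 where added. Each cell is hold probability (%) / average sample size.

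| True rate | Table 2 | Looks 3,5,7,9 | Looks 2,3,5,7,9 | Looks 4,6,8,10 | Looks 2,4,6,8,10 |
|---|---|---|---|---|---|
| 15% | 7.1 / 9.8 | 8.36 / 9.52 | 8.36 / 9.50 | 7.16 / 9.78 | 8.21 / 9.65 |
| 25% | 26.5 / 9.2 | 25.19 / 8.68 | 25.19 / 8.62 | 26.58 / 9.18 | 28.04 / 8.91 |
| 30% | 39.6 / 8.7 | 36.25 / 8.14 | 36.25 / 8.05 | 39.49 / 8.75 | 40.89 / 8.40 |
| 45% | 76 / 7.2 | 70.34 / 6.32 | 70.34 / 6.12 | 76.17 / 7.17 | 76.90 / 6.58 |

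Looks at 4, 6, 8, 10 reproduce both columns of Table 2 to within simulation and rounding error. The stated schedule does not, and adding a look at 10 to it does not help (42.15% at a 30% rate; average size 6.32 at 45%). Under looks at 4, 6, 8, 10, a bound at n=2 raises the hold probability slightly. Also enforcing Table 1's bound at 3 gives 10.30% at a 15% rate and 30.96% at 25%.

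**Which rule acts at 2/2 in the expansion.**

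- *3 patients already at the RP2D.* They had no DLT, because 1 of 3 would have required 3 more patients. The data at the dose level are now 2 of 5, within its first 6, so Appendix F suspends accrual.
- *6 patients already at the RP2D.* The Appendix F count is used up. Section 6.1.4 is triggered but asks only for discussion. Section 9.4.4 has no boundary yet.

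**The case against.** The strongest reply is that a first look at 3 is an ordinary choice, that other rules and oversight cover this path, and that the gain is tiny. Much of that stands.

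- A reader might infer from Section 9.4.4 that a third patient will always be infused after 2/2. The documents do not support that. With 3 patients at the RP2D, Appendix F suspends accrual first. With 6, the discussion trigger in Section 6.1.4 and the investigators' continuous monitoring in Section 10.1.5 could lead to a pause, though neither orders one.
- A reader might infer that the dose has already failed. The 9.4.4 rule counts expansion patients only. With the same prior, pooling the earlier patients gives 0.526 for 2/5, 0.333 for 2/8 and 0.584 for 3/8, all below 0.65.
- A reader might infer that the expansion is less protective than the escalation, because Section 9.4.2 says "a minimum of two subjects and a maximum of 18 subjects will be enrolled". That minimum suggests that 2 of 2 can end a level, but 9.4.2 states no such action and allows three patients to be enrolled concurrently. The earlier data at the dose also differ.
- Timing limits the benefit. Patients arrive about 35-42 days apart, the DLT window runs to 56 days, and no wait between expansion patients is stated. Patient 3 may be infused 14-21 days before patient 2's window closes. In partial answer, Section 8.3.1 notes that cytokine release syndrome typically occurs in the first 7 days after other cell therapies, so such a DLT would usually be known in time.
- If the first look is really at 4, as Table 2 implies, 2/2 does not make a hold certain, since 2/4 gives 0.601.

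What remains is that 2/2 exceeds the plan's own limit under either schedule, and that with 6 patients already at the RP2D no written rule orders a hold at that point.

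**Conclusion.** The point holds as a small gap in Section 9.4.4. The 65% criterion is met at 2/2 (75.6%), Table 1 gives no boundary there, and with the look at 3 that the text and table state, patient 3 cannot change the decision. The gap is open when 6 patients were already treated at the RP2D. This rests on reading Appendix F's wording on any dose level as covering expansion patients.

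Under the stated schedule the benefit is at most p² patients on average: 0.06 at a 25% DLT rate, 0.09 at 30% and 0.20 at 45%. These are upper bounds, because they assume that patient 2's DLT is known before patient 3 is infused.

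A reader might also infer that the change is free. That is true only for looks at 3, 5, 7, 9, where the hold probability does not move. Under looks at 4, 6, 8, 10, an n=2 bound raises it from 7.2% to 8.2% at a 15% rate and from 26.6% to 28.0% at 25%. Enforcing the bound at 3 as well gives 10.3% and 31.0%.

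**What to change.** 1. In Section 9.4.4, apply the existing 65% criterion from the second expansion patient: change the first column of Table 1 from 3 to 2-3, bound 2, and amend the monitoring sentence to match.
2. State the look schedule explicitly and recompute both columns of Table 2 for it.
3. Reconcile Section 9.4.4 with the Dose-Expansion Cohorts text in Section 6.1.4 and with Appendix F. Say which rules apply to expansion patients, whether patients from the escalation count, and what each trigger does. Which rule governs is for the sponsor to settle.

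The cost is one column label, a few sentences and a short recomputation of Table 2. If the schedule is 3, 5, 7, 9, the added bound leaves the hold probability unchanged. If it is 4, 6, 8, 10, the sponsor accepts the slightly higher hold probabilities given above.
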